13.5.2.4 Sensitivity Analyses for Primary Efficacy Analysis

A number of sensitivity analyses will be performed for the primary endpoint, annualized rate of VOCs, to examine the robustness of the results:

1. Sensitivity analysis will be conducted on the mITT and PP analysis sets

- 2. Sensitivity analysis using negative binomial regression (or Poisson regression as appropriate) with total number of VOCs as dependent variable, log treatment exposure as an offset, stratification factors and treatment as independent variables. The analysis will be performed on the ITT, mITT and PP analysis sets.

- 3. Tipping Point Analysis #1 - P-Value Frontiers

The primary analysis method for annualized rate of VOCs is stratified Wilcoxon rank-sum test. This sensitivity analysis is to explore the sensitivity of the Wilcoxon rank-sum test on the distribution of observed data.

In this tipping point analysis, the annualized rate of VOCs for the IMR-687 highest tolerated dose subjects and placebo subjects will be shifted separately (change by -50% to +50% at individual subject level) and the results (median difference, Interquartile range [IQR] and p-value) from stratified Wilcoxon rank-sum test for each combination of the shifts will be tabulated. P-Value Frontiers will be identified when the p-value has changed from non-significant to significant, or vice versa. The tipping point analysis will be performed on the ITT analysis sets.

- 4. Sensitivity analysis for Missing values due to early discontinuation

In the primary analysis of annualized rate of VOCs, there is an underlying assumption that the unobserved rate of VOCs after study discontinuation will be the same as the observed rate for the same subject. Several sensitivity analyses will be performed to examine this assumption and its impact. The analysis below will be performed on the ITT analysis set.

4.1 Completer, non-completer, and pooled analysis

The primary analysis will be repeated for subjects who completed the study treatment period and who did not separately, and combined subject populations will be analyzed, to explore the differences between the annualized rates of VOCs among completers, discontinued patients, and the combined patient group.

For the pooled analysis, a jump-to-reference (J2R) method will be applied to non-completers in order to combine them with completers. In the jumped-to-reference method, after dropout, the subject's outcomes (events of VOC) are assumed to "jump" to those of the reference group (completers in the placebo group).

For a subject in the IMR-687 dose groups who dropout, the annualized rate of VOCs will be recalculated as:

$$[\text{Total number of observed VOCs during treatment period} + \text{annualized rate from Placebo completers} * (\text{Date of expected last study drug if not discontinued} - \text{Date of last dose of study drug} + 1)] / 365.25$$

The annualized rate from Placebo completers will be the median (or average when median is 0) rate of all Placebo completers. Date of expected last study drug if a subject is not discontinued is calculated as First Dose Date + 364 days (52 weeks). Dropout subjects in the Placebo group will not require additional imputation.

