4.2 Tipping Point Analysis #2 – MNAR with J2R

This tipping point analysis will be based on the J2R reference imputation, where the reference refers to the average annualized rate of VOCs among the completers in the placebo group in Section 4.1 Assuming the p-values for the primary comparison (highest tolerated dose vs placebo) are still significant with J2R (using prorogated alpha from IA), incremental changes (delta) in the referenced rate will be applied to the periods deemed to be MNAR, for the dropout subjects in the IMR-687 dose groups. If during the course of incrementing delta, the study conclusions change from favorable to unfavorable for the IMR-687 highest tolerated dose group, a tipping point is reached. The delta change will start from 0, and increment at a rate of 0.5 event/year, but granularity can be adjusted by incrementing by smaller or large amounts as needed.

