4.3 Multiple Imputation Under MAR

For the discontinued subjects, alternative to the J2R method, the annualized rate of VOCs after dropout will be imputed using multiple imputation under MAR. MAR assumes the missing value is independent of unobserved outcomes given observed data (i.e., annualized rate of VOCs after dropout can be modeled based on subjects with observed annualized rate of VOCs).

The following steps will be implemented:

Step 1:

A fully conditional specification (FCS) method will be used to impute the missing annualized rate of VOCs after dropout using a regression model. The regression will include the covariates of treatment, observed number of VOCs, duration in the study, region (North America/Europe vs. Africa/Middle East) and HU use (Yes vs. No). Missing data imputation will be performed using the SAS PROC MI procedure. Refer to [Appendix 6](#) for the order of variables in the model.

Step 2:

For each of the repetitions in the datasets, the total number of VOCs for the entire study will be recalculated for the dropouts as:

$$[\text{Total number of observed VOCs during treatment period} + \text{annualized rate of VOCs after dropout} * (\text{Date of expected last study drug if not discontinued} - \text{Date of last dose of study drug} + 1)]/365.25$$

Step 3:

The negative binomial regression (or Poisson regression as appropriate) with total number of VOCs as dependent variable, log treatment exposure as an offset, stratification factors and treatment as independent variables will be run for each of the 100 datasets to obtain 100 estimators of interest.

Step 4:

Use SAS PROC MIANALYZE to produce an overall pooled estimate (mean of 100 estimates)

The multiple imputation sample code is specified in [Appendix 6](#). However, there could be certain adjustments due to unexpected data issues after unblinding treatment. All post-unblinding modifications to the multiple imputation model or approaches to address missing data will be described in the CSR.

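### The J2R and multiple-imputation formulas divide observed VOCs by 365.25; relative to a correct J2R this always favours IMR-687, and Tipping Point #2 inherits it

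*SAP*

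**What the plan says.** SAP Section 13.5.2.1 defines the primary endpoint as the VOC count divided by years on study drug. Section 13.5.2.3 assumes that a subject's unobserved rate after discontinuation equals the observed rate. Section 13.5.2.4 item 4 sets out the analyses meant to test that assumption.

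- **Item 4.1 (J2R).** "For a subject in the IMR-687 dose groups who dropout, the annualized rate of VOCs will be recalculated as" [observed VOCs + reference rate × (expected last dose date − actual last dose date + 1)] / 365.25. The expected last dose date is the first dose date plus 364 days. On the reference: "The annualized rate from Placebo completers will be the median (or average when median is 0) rate of all Placebo completers". On the control arm: "Dropout subjects in the Placebo group will not require additional imputation".
- **Item 4.2 (Tipping Point #2).** It is built on the J2R imputation, but "where the reference refers to the average annualized rate of VOCs among the completers in the placebo group". Its entry condition is "Assuming the p-values for the primary comparison (highest tolerated dose vs placebo) are still significant with J2R". On the increments: "The delta change will start from 0, and increment at a rate of 0.5 event/year".
- **Item 4.3 (multiple imputation), Step 2.** "the total number of VOCs for the entire study will be recalculated for the dropouts as" the same bracketed expression, with the imputed rate in place of the reference. Step 3 fits a negative binomial (or Poisson) model with "log treatment exposure as an offset, stratification factors and treatment as independent variables will be run for each of the 100 datasets". Appendix 4 defines exposure as first to last dose of study drug, and nothing gives imputed subjects a longer period.

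Appendix 6 has no code for either recalculation, so nothing there corrects the printed formulas.

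**The concern.** Rate times days must be divided by 365.25 to become events. The observed count is already in events and must not be. Because the bracket closes before the divisor, each observed VOC is reduced to 1/365.25 = 0.0027. That conflicts with Section 13.5.2.1, and with item 4.3's own description of its Step 2 result as a total count.

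In J2R the loss falls on IMR-687 dropouts only, so the error has one direction relative to a correct J2R. Protocol Section 8.5 requires a subject who stops study drug to leave the study, so later VOCs are largely unobserved. Items 4.1 to 4.3 are the SAP's check on that gap. A J2R that discards the VOCs observed on drug can endorse a result that a correct J2R would question. It also gives Tipping Point #2 an entry condition that is too easy to meet and a starting point that is too low.

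**Working it through.** **Notation.** O = observed VOCs, R = reference rate per year, T = study day of last dose. By the SAP's dates the expected last dose is Day 365. The printed remaining days are d = 365 − T + 1, and the true remaining days are m = 365 − T.

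- Printed J2R: (O + R·d) / 365.25
- Correct J2R: (O + R·m/365.25) / (365/365.25)

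The SAP gives no worked J2R or imputation value to reproduce. Its power figures, the source of the simulation inputs, do reproduce. A noncentral t calculation with sample sizes divided by π/3, difference 2.034 and SD 2.7 gives 0.886 (31 vs 49) and 0.788 (24 vs 37), against 0.880 and 0.776 in Appendix 7.

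**Single subjects.** R = 5, T = 180, so d = 186 and m = 185.

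| Observed VOCs | Printed | Correct |
|---|---|---|
| 0 | 930/365.25 = 2.55 | 2.53 |
| 2 | 932/365.25 = 2.55 | 4.54 |
| 3 | 933/365.25 = 2.55 | 5.54 |
| 6 | 936/365.25 = 2.56 | 8.54 |

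The printed formula barely distinguishes no crises from six. Over O = 1 to 14, R = 0 to 30 and T = 1 to 364 it is below the correct value every time, by at least 0.92 per year. A subject whose observed rate equals the reference of 5 should stay at 5.0. For last dose on Day 90, 180 or 270 the printed formula gives 3.78, 2.55 or 1.32, roughly the reference times the share of the year remaining.

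**Whole-trial effect.** From the documents: 49 vs 31 subjects, 12 and 7 dropouts (SAP Table 1), SD 2.7, rates of 5 and 3 per year, two-sided 0.0494. Assumed: gamma-Poisson counts, dropout unrelated to outcome, uniform dropout timing within each window, and four equal strata for the stratified test. There were 10,000 trials per scenario, with the placebo-completer median as reference. Entries are the percentage significant in favour of IMR-687, as primary / printed J2R / corrected J2R; ranges span unstratified and stratified Wilcoxon tests.

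| Last dose of dropouts | No true effect | True 3 vs 5 |
|---|---|---|
| Days 1–364 | 2.3–2.5 / 11.2–11.5 / 1.1–1.2 | 89–90 / 95 / 80–82 |
| Days 1–90 | 2.2–2.5 / 0.9–1.1 / 0.3–0.4 | 78–79 / 51–53 / 42–45 |
| Days 1–168 | 2.5 / 3.0 / 0.6–0.7 | 83–84 / 74–75 / 61–63 |
| Days 168–364 | 2.3 / 29–30 / 1.8–1.9 | 93 / 99.5 / 91–92 |

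With 10% dropout and no true effect (unstratified, same row order): 2.2 / 4.2 / 1.6, 2.4 / 1.6 / 1.2, 2.3 / 2.4 / 1.4 and 2.5 / 8.2 / 2.2. Printed J2R was significant more often than corrected J2R in all 16 unstratified and 8 stratified scenarios.

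**Tipping Point #2** (true 3 vs 5, 25% dropout, 1,000 trials per timing, all IMR-687 dropouts treated as MNAR). Given a significant primary result, the entry condition was met in 99 vs 90%, 66 vs 56%, 87 vs 73% and 100 vs 98% of trials (printed vs corrected, same row order). The printed tipping delta exceeded the corrected one by a median of 4.0, 0.5, 1.0 and 8.0 events per year, against the SAP's step of 0.5. These medians cover only trials where both versions met the entry condition and tipped by 30 per year.

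**Multiple imputation.** With O = 3, T = 180 and an imputed rate of 5, the Step 2 total is 933/365.25 = 2.55 as printed, against 3 + 5 × 185/365.25 = 5.53. Dropouts in all arms are affected. Under no effect, uniform timing and exposure to last dose, an average dropout contributes about 2.5 events over 0.5 year, so the expected rate ratio stays at 1.00. Changing only the offset to 52 weeks, with 35% active and 25% placebo dropout, gives (0.65×5 + 0.35×2.5)/(0.75×5 + 0.25×2.5) = 4.125/4.375 = 0.94, and 1.06 with the arms reversed. Changing only the bracket gives [5/(0.65 + 0.35×0.5)]/[5/(0.75 + 0.25×0.5)] = 6.06/5.71 = 1.06. Count and offset must be corrected together.

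**The case against.** Several points on the other side are fair.

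- **Direction.** The claim holds against a correct J2R, not against the primary analysis. With R = 5, a dropout observed at 3 per year falls below the primary value only from about Day 148. With dropout by Day 90, printed J2R is still stricter than the primary. This stands and limits the claim.
- **Size.** The documents give 25% dropout but no timing, and the results depend heavily on timing. The simulated percentages are illustrations. They are not trial error rates, because J2R is not a route to success. This also stands.
- **Tipping Point #2.** Item 4.2 prints no formula and names the average as reference where item 4.1 names the median, so its start need not equal the item 4.1 value. It still inherits the bracket through J2R. The two references were about 5.0 and 4.7 per year in the simulation, and the choice moved the corrected no-effect percentage by at most 0.2 points.
- **Offset.** Step 3 does not say outright that imputed dropouts keep their actual exposure. Appendix 4's definition points that way, and no other period is given.
- **Readable intent.** A programmer might notice the units. But the bracket is printed identically twice and no code corrects it. A repair after unblinding would be a discretionary change to a pre-specified analysis.

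**Conclusion.** The formulas in items 4.1 and 4.3 are wrong as printed. In J2R, each IMR-687 dropout with at least one VOC receives a rate too low by almost exactly that subject's VOC count, compared with a correct calculation. Dropouts without VOCs are essentially unaffected. The analysis is therefore too lenient to IMR-687: slightly if dropout is early or rare, severely if it is late. With no true effect, 25% dropout and last doses after Day 168, it is significant for the drug in 29–30% of simulated trials against 1.8–1.9% when corrected. Those sizes rest on the assumed timing, count distribution and outcome-independent dropout; the direction of the J2R error does not. The multiple-imputation error has no fixed direction.

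The primary analysis, alpha, success rule, negative binomial analysis on observed data, Tipping Point #1 and the separate completer and non-completer analyses are unaffected. This should be fixed, but it does not threaten the primary result itself.

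**What to change.** 1. **J2R (item 4.1).** Rate = [observed VOCs + reference rate × remaining days/365.25] / (planned treatment days/365.25). Remaining days = expected minus actual last dose date. Drop the +1, which counts the last dose day twice.
2. **Tipping Point #2 (item 4.2).** Start from this corrected J2R. Name one reference, median or average of placebo completers, and use it in both items.
3. **Multiple imputation, Step 2.** Total VOCs = observed VOCs + imputed rate × remaining days/365.25.
4. **Multiple imputation, Step 3 and Appendix 6.** For imputed subjects, set the offset to the log of the full planned period, so that count and exposure match. Define that period once: first dose plus 364 days spans 365 days inclusive, whereas 52 weeks is 364.

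The cost is SAP wording and programming, with no new data and no change to the primary analysis. Corrected J2R results will look less favourable to IMR-687, which is a reason to make the change before unblinding.

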4.2 Tipping Point Analysis #2 – MNAR with J2R

This tipping point analysis will be based on the J2R reference imputation, where the reference refers to the average annualized rate of VOCs among the completers in the placebo group in Section 4.1 Assuming the p-values for the primary comparison (highest tolerated dose vs placebo) are still significant with J2R (using prorogated alpha from IA), incremental changes (delta) in the referenced rate will be applied to the periods deemed to be MNAR, for the dropout subjects in the IMR-687 dose groups. If during the course of incrementing delta, the study conclusions change from favorable to unfavorable for the IMR-687 highest tolerated dose group, a tipping point is reached. The delta change will start from 0, and increment at a rate of 0.5 event/year, but granularity can be adjusted by incrementing by smaller or large amounts as needed.

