8.1.2 Power Estimation

Annualized rate of VOCs was changed from a key secondary endpoint in Protocol 4.0/4.1 (April 2021) to the primary efficacy endpoint in this SAP and in Protocol Amendment 5.0/5.1 (February 2022). The power calculation below was based on the projection that there will be approximately 49 randomized subjects in higher dose, 35 subjects in lower dose and 31 subjects in placebo group.

Assuming that the actual data distribution is normal when the significance level (alpha) of the test is 0.050, the standard deviation is 2.7 in both groups, and there are no dropouts, there will be 88% power to detect a difference between the medians of 5.0 and 3.0 for the placebo and the IMR-687 highest tolerated dose groups, respectively (i.e., a 40% difference), using a two-sided Wilcoxon Rank-Sum test ([Table 1](#)). Assuming a 25% dropout rate, the power will be 78%.

Table 1 Power Estimation

| Scenarios | N for IMR-687 Highest Tolerated Dose | N for Placebo | Significance Level (two-sided alpha) | Standard Deviation | Difference | Power |
|------------------------|--------------------------------------|---------------|--------------------------------------|--------------------|------------|-------|
| No Dropout | 49 | 31 | 0.05 | 2.7 | 40% | 88% |
| With 25% Dropout Rate* | 37 | 24 | 0.05 | 2.7 | 40% | 78% |

* estimated based on Ataga et al.

The power calculation for the Annualized rate of VOCs was carried out in PASS Version 2020 v20.0.3. See [Appendix 7](#) for details.

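### SAP 13.5.2.4 items 4.1 and 4.2 define the same placebo reference rate differently (median versus average), so the tipping-point analysis at delta = 0 need not reproduce the jump-to-reference result it starts from

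*SAP*

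**What the plan says.** SAP 13.5.2.4 item 4.1 applies J2R to active-arm subjects who stop early. Their observed VOCs are kept, and VOCs for the remaining time up to Week 52 are added at a placebo reference rate. Placebo dropouts are not imputed. The reference is defined as follows: "The annualized rate from Placebo completers will be the median (or average when median is 0) rate of all Placebo completers".

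Item 4.2 is the second tipping-point analysis. It is tied to item 4.1 in three ways:

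- It declares its basis: "This tipping point analysis will be based on the J2R reference imputation".
- It is carried out on the premise that the p-values for the highest tolerated dose against placebo "are still significant with J2R (using prorogated alpha from IA".
- It moves away from that result in steps: "The delta change will start from 0, and increment at a rate of 0.5 event/year".

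Item 4.2 also points to Section 4.1 for the reference. But it describes the reference with another statistic: "the reference refers to the average annualized rate of VOCs among the completers in the placebo group".

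The SAP gives no skewness for VOC rates. The only distribution it states is the normal one in the power calculation (8.1.2 and Appendix 7), where "the standard deviation is 2.7 in both groups".

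**The concern.** A delta-adjusted tipping-point analysis is read as a distance: how far the imputed rate must move from the reference before the conclusion changes. That reading needs delta = 0 to be the J2R analysis. Here the condition for running item 4.2 is assessed with one reference (the median), and the search starts from another (the average).

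Two things follow. The tipping delta is measured from a point that is not the reported J2R result. It is also possible for J2R to be significant under item 4.1 while delta = 0 under item 4.2 is already non-significant, and the SAP does not say what would then be reported.

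Subjects who stop study drug must also leave the study (Protocol 8.5), so their later VOCs are not observed. The SAP allows for 25% dropout and classes most discontinuation reasons as missing not at random (Table 8). Items 4.1 and 4.2 are its analyses that impute post-dropout events under such a mechanism. The reference is computed from placebo data by arm, so if the statistic is left open it would be chosen after unblinding.

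**Working it through.** **1. The two definitions side by side**

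| | Item 4.1 (J2R) | Item 4.2 (tipping point) |
|---|---|---|
| Subjects | placebo completers | placebo completers |
| Statistic, median > 0 | median | average |
| Statistic, median = 0 | average | average |

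The two agree when the median is 0 or when mean and median happen to be equal. Otherwise they differ.

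**2. The plan's own figures**

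The SAP gives no figure for J2R or the tipping point, so the planning values were checked first. Inputs are 31 placebo and 49 highest-dose subjects (24 and 37 after 25% dropout), means 5.034 and 3, SD 2.7, two-sided alpha 0.05 (8.1.2 and Appendix 7). Each n is multiplied by the Wilcoxon efficiency 3/π = 0.955, and power is taken from the noncentral t with noncentrality (2.034/2.7)/√(1/n1 + 1/n2).

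- 31 and 49 become 29.60 and 46.79; noncentrality 3.21; power 0.886. Direct simulation of the rank-sum test gives 0.884. The SAP states 0.880.
- 24 and 37 become 22.92 and 35.33; noncentrality 2.81; power 0.788. Simulation gives 0.784. The SAP states 0.776.

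Both agree within 2 points.

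**3. Size of the gap**

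For each scenario, 40,000 sets of 24 placebo completers were drawn. The gap is the item 4.2 reference (mean) minus the item 4.1 reference (median, or mean if the median is 0), in VOCs per year. Under the SAP's normal distribution the average gap is 0.00, and the median lies below the mean in 49% of sets. With gamma-Poisson (negative binomial) counts of mean 5.034:

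| SD | Source of SD | Average gap | Gap / 0.5 step | Median below mean |
|---|---|---|---|---|
| 2.7 | SAP | 0.30 | 0.6 | 73% |
| 3.5 | assumed | 0.60 | 1.2 | 86% |
| 4.5 | assumed | 1.06 | 2.1 | 94% |
| 6 | assumed | 1.87 | 3.7 | 99% |

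The two references differ at all in 97% of sets at SD 2.7 and in nearly all sets at SD 6. At SD 2.7 the population median and mean rates are almost equal (5.02 and 5.05 per year), so the 0.30 there reflects the sample median of 24 discrete counts. With mean 1.5 and SD 2.7 the median is 0 in 58% of sets, and the references then coincide.

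For a subject whose last dose is 168 days after the first, the imputed time is 364 − 168 + 1 = 197 days, or 197/365.25 = 0.539 year. A gap of 0.30 to 1.87 per year is then 0.16 to 1.0 VOC.

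**4. Effect on a conclusion**

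Trials were simulated with gamma-Poisson counts, means 5.034 and 3.0, 31 and 49 subjects, 25% dropout uniform over days 28 to 336, and an unstratified rank-sum test at 0.0494. Item 4.1's formula was read as observed VOCs plus rate × missing days/365.25. As printed, it divides the observed count by 365.25 too.

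Among trials significant under the median-based J2R, the average-based delta = 0 analysis had already lost significance in about 3% (SD 2.7), 7% (SD 3.5), 13% (SD 4.5) and 24% (SD 6). A repeat with other random draws agreed within about 2 points. The reverse disagreement occurred in under 0.5% of trials.

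**The case against.** **It may be loose wording.** Item 4.2 points to Section 4.1, and item 4.1 itself contains the word average. One can read item 4.2 as importing item 4.1's reference whole, and then no numerical gap exists. That reading is possible, but a programmer following item 4.2 literally would use the mean, and nothing in the SAP says otherwise. The text needs settling either way.

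**The median is defensible for a rank test.** The analysis being repeated is a Wilcoxon test, which Table 7 describes in terms of medians. A subject imputed at the median sits mid-way in the reference group, whereas the mean can place that subject somewhat above the middle under skew. This stands as a reason not to call the median an error in itself. What is wrong is the inconsistency.

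**Stronger readings that the documents do not support.** A reader might infer that the median necessarily penalises active-arm dropouts too little. That requires right skew, which the documents do not state, and their normal assumption implies none. Skew is plausible: counts cannot be negative, the SAP plans a negative binomial sensitivity analysis, and item 4.1 provides for a median of 0. It remains an assumption.

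A reader might also infer that the gap rivals the first delta step. At the only SD in the documents it is about 0.3 against 0.5; larger gaps need SDs that the documents do not give. Nor does the SAP call this its main stress test for dropout. It also plans negative binomial regression, p-value frontiers, completer and non-completer analyses, and multiple imputation.

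**Conclusion.** The inconsistency is real and is in the text: one reference, two statistics, with the precondition for item 4.2 resting on one and its starting point on the other. Unless the two coincide, delta = 0 does not reproduce J2R.

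At the planning SD of 2.7 the consequence is small: about 0.3 VOC/year on average, and about 3% of trials that pass under the median already fail at delta = 0. It grows to about 1.9/year and 24% at an assumed SD of 6. These figures rest on assumed gamma-Poisson rates with mean about 5/year, 24 placebo completers for the gap, and 25% dropout for the trial-level percentages. Under normal rates the two references still differ in any one sample, but with no systematic direction.

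Only sensitivity analyses are affected. The primary rank-sum analysis does not use the reference rate. This is a minor correction, worth making because it removes a choice that would otherwise be made with arm-level data in view.

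**What to change.** Before unblinding, name one statistic in both items and add a sentence that delta = 0 in item 4.2 is the J2R analysis of item 4.1.

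The mean rate of placebo completers is the natural choice. Item 4.1 multiplies the rate by missing time and adds the product to an event count, so the product acts as an expected count. Using the mean also removes the jump in the present rule, under which a median of 0 imputes the average while a small positive median imputes that small value. If the sponsor prefers the median because the test is rank-based, item 4.2 should say median, with the same fallback.

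The cost is a few words and no new data. Under skew, moving to the mean makes J2R slightly less favourable to active drug. In a gamma-Poisson simulation with means 5 and 3, SD 2.7, 31 and 49 subjects and 25% dropout at uniform times, J2R was significant in 81.0% of runs with the median and 78.7% with the mean. The units of item 4.1's formula can be corrected in the same edit.
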